1. PURPOSE OF THE STUDY

a. Brief Summary

For patients who undergo spine surgery or are experiencing back pain, mobilization is an important factor in long-term medical and psychological wellbeing. Unfortunately, there is currently no established objective method such that surgeons can track their patients' mobilization progress postoperatively. We hypothesize the ability of the patient to be able to track their own activity and discuss with their surgeon objective mobilization goals will not only help patients achieve empowerment in their own care but also improve their overall satisfaction and self-reported outcomes. The purpose of this study is to test our hypothesis using the most prevalent commercially available wearable technology, the Apple Watch.

b. Objectives

In this study, we will address the following questions:

1. Is it feasible for spine patients to wear the leading commercially available device (specifically, the Apple Watch) before and after spine surgery to assist with their spine care?
2. Do objective patient metrics (steps, distance traveled, max HR achieved) obtained from this commercially available device directly correlate with subjective patient reported outcome measures (PROMs) for spine surgery patients?
3. Do we see a significant change in objective outcome metrics before and after spine surgery?
4. Are patients more satisfied with their spine care as a result of using the Apple Watch in our practice?

c. Rationale for Research in Humans

The purpose of this study is to assess the efficacy of using a commercially available wearable activity monitor (the Apple Watch) in the postoperative care of patients undergoing spine surgery.

2. STUDY PROCEDURES

a. Procedures

This study protocol is similar in parts to previously approved protocol, "Accelerometers in spine surgery study," for which [name] (Co-PD on current proposal) is the PD.

All English-speaking adult patients (≥ 18 years old) who are undergoing elective spine surgery (excluding patients with spine trauma, tumors, or infection) for Cohort 1 or are undergoing any back treatment for Cohort 2 by neurosurgery attending physicians at Stanford ([name], [name], [name], [name], [name], [name]) will be eligible for participation in this study.

All participants in Cohort 1 and Cohort 2 will receive our standard of care.

In Cohort 1, percentage for random assignment to each group is 50%. Those assigned to the "intervention" (i.e., the Apple Watch) will receive instructions on how to use the activity section within the Watch. The participants will either have their mobility data submitted via the previously approved app Neurocoach. The intervention group will wear the Apple watch 2-6 weeks pre-operatively as well as at least 6 months post-operatively (may continue to wear as long as 12 months). The control group will not. Patients in the interventional group receiving an Apple Watch may be asked to come in for a training and set-up visit at clinic. Parking passes will be provided for this visit.

All patients in Cohort 1 will be seen in follow-up clinic as per standard of care (4-6 weeks, 3 months, 6 months, and 12 months post-operatively). At each time point, all patients will complete standardized quality of life questionnaires (several of which are already incorporated in our postoperative clinic) and an additional study-specific questionnaire regarding satisfaction with their care and recovery.

In Cohort 2, all participants will receive an Apple Watch and instructions on how to use the activity section within the Watch. The participants will have their mobility data submitted via the previously approved app Neurocoach. Participants will wear the Apple Watch for 2-3 weeks. Participants will complete standardized quality of life questionnaires (several of which are already incorporated in our postoperative clinic) at the beginning and end of the 2-3 week study. This cohort will have their pain monitored daily using brief questionnaires.

b. Procedure Risks

Our protocol does not change the standard of care for any patient. It provides a supplementary intervention for half of our patients. The intervention is using a wearable activity monitor device (the Apple watch), which is a minimal risk.

c. Use of Deception in the Study

Deception will not be used.

d. Use of Audio and Video Recordings

Audio or video recording will not occur.

e. Alternative Procedures or Courses of Treatment

Standard of care will not be withheld. Our study does not involve alternative procedures or treatments.

f. Will it be possible to continue the more (most) appropriate therapy for the participant(s) after the conclusion of the study?

All patients will undergo standard of care for their spine surgery before, during, and after the study.

g. Study Endpoint(s)

For Cohort 1, the study endpoint will be 12 months postoperatively. Following enrollment during the pre-operative visit, we will see patients in clinic during their standard postoperative visits, at 4-6 weeks, 3 months, 6 months, and 12 months post operatively. All patients will complete the Stanford Spine quality of life questionnaires, as per the standard of care, at all postoperative visits. Patients with the Apple Watch will also fill out a paper questionnaire assessing satisfaction with the Apple Watch (all questions are included in attachment).

As participants reach the 12-month study period, we will conduct ongoing analysis of the data. If we observe clear statistically significant and clinically significant superiority in one group, the study will be terminated prior to the projected total participant population has been enrolled. If there are no such differences noted, the Cohort 1 will terminate after the all patients have had their 12-month postoperative visit, likely July 2023.

For Cohort 2, the study endpoint will be 2-3 weeks after enrollment and Apple Watch setup. If we observe clear statistically significant and clinically significant changes, the study will be terminated prior to the projected total participant population has been enrolled. If there are no such differences noted, the Cohort 2 will terminate after all patients have completed the study, likely August 2021.

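### Cohort 1 quality-of-life questionnaires are scheduled only after surgery; adding or naming a pre-randomisation form would be a minor, cheap gain in precision

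*Protocol*

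**What the plan says.** Protocol section 2.a states that Cohort 1 patients "will be seen in follow-up clinic as per standard of care (4-6 weeks, 3 months, 6 months, and 12 months post-operatively"). The next sentence ties the forms to those times: "At each time point, all patients will complete standardized quality of life questionnaires (several of which are already incorporated in our postoperative clinic"). Section 2.g repeats the schedule: "All patients will complete the Stanford Spine quality of life questionnaires, as per the standard of care, at all postoperative visits".

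Section 2.g also describes the preoperative contact, "Following enrollment during the pre-operative visit, we will see patients in clinic during their standard postoperative visits", but assigns no questionnaire to it. Section 5.a.vii (Psychological well-being) refers again to forms at each time point, adds no preoperative one, and relies on the forms to show whether the Watch is harming patients.

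The Watch is issued well before surgery: "The intervention group will wear the Apple watch 2-6 weeks pre-operatively as well as at least 6 months post-operatively". The order of randomisation, Watch issue and any preoperative form is not given.

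The hypothesis in section 1.a is that self-tracking and discussion of goals "will not only help patients achieve empowerment in their own care but also improve their overall satisfaction and self-reported outcomes". Section 4.a plans 100 patients per arm.

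**The concern.** Followed as written, the schedule yields no quality-of-life score before randomisation in Cohort 1. The hypothesis on self-reported outcomes implies a comparison of these scores between the arms, and section 5.a.vii uses the same forms to look for a detrimental effect of the Watch. Without a baseline, neither use can adjust for where patients started, and change from a patient's own starting level cannot be described.

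When data are collected is a matter for the protocol. An SAP can choose the model, but it cannot supply a score that was never collected, and a missed pre-randomisation form cannot be recovered later.

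Timing matters too. A form completed just before surgery may fall within the 2-6 weeks of preoperative Watch wear. In the Watch arm it would then no longer be a pre-intervention score, and adjusting for it could remove part of any effect. The baseline has to precede randomisation and Watch issue, not merely surgery.

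**Working it through.** **Is a baseline form scheduled?**

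| Protocol section | Cohort 1 quality-of-life forms |
|---|---|
| 2.a Procedures | at the four postoperative times |
| 2.g Study Endpoint(s) | at all postoperative visits; enrolment visit named, no form assigned |
| 5.a.vii Psychological well-being | at each time point; none added |
| 4.k Payments | control patients paid per questionnaire visit; amounts redacted, so the number of visits cannot be inferred |

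No preoperative form is scheduled, and none is ruled out.

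**What would a baseline be worth?** The protocol states no alpha, power, effect size or SD, so it has no sample-size figure to reproduce.

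Inputs:
- From section 4.a: n = 100 per arm.
- Assumed: two-sided alpha 0.05, 80% power, full follow-up, and a correlation r between baseline and follow-up score, shown over a range.

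Adjusting for baseline multiplies the residual variance by (1 - r²). In SD units the normal approximation for the detectable difference is

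(1.960 + 0.842) × sqrt(2(1 - r²)/n).

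With r = 0 this is 2.802 × sqrt(0.02) = 0.396. The noncentral t distribution (df 2n - 2 unadjusted, 2n - 3 with the covariate) gives the slightly larger values below. The equivalent unadjusted sample size is 100/(1 - r²) per arm.

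| r | 1 - r² | Detectable difference (SD) | Equivalent n per arm |
|---|---|---|---|
| no baseline | 1.00 | 0.398 | 100 |
| 0.2 | 0.96 | 0.390 | 104 |
| 0.3 | 0.91 | 0.380 | 110 |
| 0.5 | 0.75 | 0.345 | 133 |
| 0.6 | 0.64 | 0.319 | 156 |

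**Is the postoperative-only comparison biased?** 5,000 trials were simulated at each of r = 0.3, 0.5 and 0.7, with 100 per arm, a true effect of 0.30 SD and full follow-up.

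| r | Mean estimate, unadjusted | Mean estimate, adjusted | SD of estimate, unadjusted | SD of estimate, adjusted |
|---|---|---|---|---|
| 0.3 | 0.299 | 0.299 | 0.142 | 0.136 |
| 0.5 | 0.294 | 0.298 | 0.141 | 0.123 |
| 0.7 | 0.302 | 0.302 | 0.141 | 0.100 |

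Both estimators centre on the true value; only the spread differs.

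**Covariate or change score?** Relative to the postoperative-only comparison, a simple change score has variance 2(1 - r). That is 1.40 at r = 0.3, 1.00 at r = 0.5 and 0.80 at r = 0.6, against 0.91, 0.75 and 0.64 with the baseline as a covariate. Below r = 0.5 a change score is worse than using no baseline, so the gain in the first table depends on covariate use.

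**The case against.** The strongest reply is that the protocol is silent rather than wrong. Section 2.g calls the questionnaires standard of care, section 2.f says "All patients will undergo standard of care for their spine surgery before, during, and after the study", and the questionnaire attachment is not available. Routine care may already collect these forms before surgery. This stands in part, and it is why the point is conditional. Still, 2.g speaks of standard of care for the forms only at postoperative visits, and 2.f answers a question about continuing therapy. Neither states that a form precedes randomisation.

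A reader might go further and infer from the remark in 2.a about forms used in the postoperative clinic that routine collection begins only after surgery. The text does not support that. The same remark is attached to the Cohort 2 forms, which are completed "at the beginning and end of the 2-3 week study" by patients who need not be postoperative. It says which forms are in use, not when their use starts.

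A reader might also see an inconsistency between the cohorts, since Cohort 2 has a starting form. It is not one. Cohort 2 has a single arm and needs a starting score to show any change; Cohort 1 has a randomised control arm and does not.

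It is also fair to object that none of the objectives in section 1.b depends on this. Feasibility and the before-and-after comparison rest on Watch data. The correlation objective can be answered from postoperative pairs of scores and metrics. Satisfaction with care as a result of using the Watch has no natural preoperative counterpart. This stands, and it limits the weight of the point.

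Finally, the size rests wholly on an assumed correlation. Surgery falls between the two measurements, and nothing in the protocol supports r of 0.5 or more. This stands too.

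**Conclusion.** The point holds as a minor, low-cost improvement. The Cohort 1 schedule contains no pre-randomisation quality-of-life form, and whether routine care supplies one is neither stated nor excluded. If none is collected, the between-arm quality-of-life comparison, and the use of the forms to detect harm from the Watch, have no baseline.

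On the stated assumptions, a baseline would lower the detectable difference only from 0.398 to 0.390 SD at r = 0.2, but to 0.345 SD at r = 0.5 and 0.319 SD at r = 0.6. The gain is negligible at the low end and useful at the high end, and the protocol does not allow a choice between them.

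It might be inferred that the arm comparison is biased or invalid without a baseline. It is not: randomisation protects it under full follow-up. If dropout were related to starting status, a baseline score would also help in handling missing data, but the protocol gives no dropout figure from which to size that.

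**What to change.** In sections 2.a and 2.g, state that every Cohort 1 patient, in both arms, completes the same quality-of-life questionnaires at the preoperative enrolment visit, before randomisation and before any Watch is issued, and that this score serves as a baseline covariate. If a routine form already meets that timing, name it as the baseline instead. The analysis model can be left to the SAP.

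The cost is one more questionnaire set at a visit patients already attend, and possibly one more control-arm payment under section 4.k. If routine care already collects the forms in time, the cost is a clarifying sentence. No preoperative form on satisfaction with care is needed.

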4. PARTICIPANT POPULATION

a. Planned Enrollment

Cohort 1:

- (I) around 200 patients total at Stanford Neuroscience Health Center and at Stanford Medicine Orthopaedic Spine Center
- (II) around 200 patients total at Stanford Neuroscience Health Center and at Stanford Medicine Orthopaedic Spine Center (the cohort will not include participants from any other non-Stanford sites)

100 patients will be in the control arm - no Apple Watch or app; 100 patients will be in the intervention arm - will receive Apple Watch and will download app.

A few additional subjects may be enrolled so as not to delay the completion of the trial. Surgery for a subject may change to several weeks later or subjects may decide not to do surgery. The target in each cohort will remain at about 100 subjects.

Participants will be adults (greater than or equal to 18 years old) who will be undergoing elective spine surgery at Stanford University Hospital by a Stanford Neurosurgery or Orthopaedic Spine attending physician. The reason for using such participants is to be able to effectively assess long-term mobility and satisfaction outcomes of patients who have undergone spine surgery who will be using Apple Watch in addition to the standard of care.

Cohort 2:

- (I) 15 patients total at Stanford Neuroscience Health Center
- (II) 15 patients total at Stanford Neuroscience Health Center (the cohort will not include participants from any other sites)

Participants will be adults (greater than or equal to 18 years old) who are undergoing any back treatment by a Stanford Neurosurgery attending physician. The reason for using such participants is to be able to effectively assess short-term mobility and satisfaction outcomes of patients experiencing back pain who will be using Apple Watch in addition to the standard of care.

b. Age, Gender, and Ethnic Background

All participants will be adults (greater than or equal to 18 years old). There is no other specification in terms of gender or ethnic background.

c. Vulnerable Populations

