Screening for eligibility will be conducted in the clinic. Patients who are scheduled for pre-operative visits and meet inclusion criteria will be eligible for enrollment. Each patient's attending surgeon will give the referral to approach each patient for recruitment into the study.

j. Participation in Multiple Protocols

It is unlikely that patients will be involved in another research study, as there are no other prospective studies that are currently enrolling spine patients in the Stanford Neuroscience Health Center. We have contacted other spine faculty in the Neurosurgery Department and none have identified any trials that participants might be enrolled in during our study period. There are retrospective reviews which do not require patient enrollment.

k. Payments to Participants

Cohort 1:

If patients in the interventional group are asked to come for an extra clinic visit for training and setup, they will receive a parking pass for the visits.

For patients in the control group (100 patients), we will compensate their time for completing questionnaires (these patients will not be provided an Apple Watch during the study). At each visit during which questionnaires are completed, the participant will receive [REDACTED], for a possible total of [REDACTED] for the entirety of the study.

Cohort 2:

Patients will be given an Apple Watch and charging cable free of charge. This must be returned to Stanford at the end of the study period. If you are asked to come for an extra clinic visit for training and setup, you will receive a parking pass for the visits.

l. Costs to Participants

Not applicable.

m. Planned Duration of the Study

- (i) Spring 2020: Obtain IRB approval for revised protocol; June 1, 2020 - May 31, 2023: Screen and enroll new patients;
- (ii) Duration of active participation in study: approximately 12 months
- (iii) June 1, 2020 - May 31, 2024: Continue collecting data, complete at least 6-month follow-up on all patients and perform interval analysis; June 1 - August 31, 2024: final data analysis.

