The greatest risk to patients in this study will be confidentiality of identifiable information. All electronic devices (e.g., computers, hard drives, thumb drives, etc.) that contain identifiable patient information will meet Stanford School of Medicine security standards; additionally, the devices will be password-protected and encrypted. The patient's activity data will be downloaded to Stanford Research IT-approved Google Firebase storage. All data will be stored per approved Research IT / DRA protocol. No data will be shared with industry partner providing part of the funding.

d. Study Conclusion

For Cohort 1, as participants reach the 12-month study period, we will conduct ongoing analysis of the data. If we observe clear statistically significant and clinically significant superiority in one group, the study will be terminated prior to the projected total participant population has been enrolled. If there are no such differences noted, the study will terminate after the all patients have had their 12-month postoperative visit, likely June 2022. We do not expect adverse effects but will be able to identify them at postoperative visits (4-6 weeks, 3 months, 6 months, and 12 months post-operatively) and intervene if needed.

For Cohort 2, we will conduct ongoing analysis of the data. If we observe clear statistically significant and clinically significant changes, the study will be terminated prior to the projected total participant population has been enrolled. If there are no such differences noted, the Cohort 2 will terminate after all patients have completed the study, likely August 2021.

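### Cohort 1 has open-ended looks with a binding superiority stop and no stricter early criterion; at an ordinary 5% level per look the false-positive rate would be about 11% to 25%

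*Protocol*

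**What the plan says.** Three places in the Protocol bear on this.

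- **Section 2.g (Study Endpoint(s)).** The looks: "As participants reach the 12-month study period, we will conduct ongoing analysis of the data". The action, which applies while recruitment is still open: "If we observe clear statistically significant and clinically significant superiority in one group, the study will be terminated". The fallback: "If there are no such differences noted, the Cohort 1 will terminate after the all patients have had their 12-month postoperative visit, likely July 2023". There is therefore a final analysis whenever no early stop occurs.
- **Section 5.d (Study Conclusion).** The same rule appears: "For Cohort 1, as participants reach the 12-month study period, we will conduct ongoing analysis of the data". The fallback carries a different date: "If there are no such differences noted, the study will terminate after the all patients have had their 12-month postoperative visit, likely June 2022".
- **Section 4.m (Planned Duration).** Enrolment runs from 1 June 2020 to 31 May 2023. Up to 31 May 2024 the team is to "Continue collecting data, complete at least 6-month follow-up on all patients and perform interval analysis".

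The planned size is in section 4.a: "100 patients will be in the control arm - no Apple Watch or app; 100 patients will be in the intervention arm". Allocation is 1:1 (section 2.a).

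The protocol does not state a significance level, the number or timing of looks, the outcome that triggers the stop, or what *clear* and *clinically significant* mean.

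**The concern.** Each look at accumulating data is a further chance of a false positive. A rule that looks as often as it likes, and must stop when the criterion is met, has an overall error rate above the level used at each look unless early looks demand stronger evidence. This rule does not ask for that.

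This is more than detail left to a statistical analysis plan. The protocol itself fixes the trigger, the binding action and the fallback. A plan that is not shown could add a boundary, but the protocol text would still commit the team to a rule without one.

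Two things are at stake. With no true effect, the trial could declare one arm superior well above the nominal rate. With a true effect, a trial that stops early does so because the estimate happened to be high, so the published effect is inflated.

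**Working it through.** **Is there a figure to reproduce?** No. The protocol states no alpha, power or effect size, so the 5% level below is an assumption.

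**Inputs from the Protocol.** 100 patients per arm (4.a); 36 months of enrolment (4.m); Watch worn 2–6 weeks before surgery (2.a), taken as about 1 month; endpoint 12 months after surgery (2.g). A patient thus yields 12-month data about 13 months after enrolment.

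**Assumptions.** Even accrual, no dropout, one outcome with SD 1, two-sided 0.05 at each look (|z|>1.96), looks only while enrolment is open, then a final test at 100 per arm.

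**Calendar.** Accrual is 200/36 = 5.56 per month. At month m the number per arm with 12-month data is 100 × (m − 13)/36. At month 36 this is 100 × 23/36 = 63.9, so about 64% of the information is available when enrolment closes.

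**False-positive rate, either arm** (simulation of the cumulative two-sample z-test, 200,000 trials per setting, stop at first crossing):

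| Looks | Interim looks + final | No clinical threshold | Early stop needs ≥0.5 SD | False Watch superiority (half of column 3) |
|---|---|---|---|---|
| Yearly | 2 + 1 | 10.9% | 9.0% | 5.4% |
| Half-yearly | 4 + 1 | 15.2% | 12.5% | 7.6% |
| Quarterly | 8 + 1 | 20.4% | 17.2% | 10.2% |
| Monthly | 22 + 1 | 25.4% | 21.6% | 12.7% |

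With quarterly looks starting only at 22 completers (7 + 1) the rate is about 18%. The last column follows from symmetry under no effect; its nominal value is 2.5%.

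**Why a clinical threshold helps little.** The smallest observed difference that reaches p<0.05 with n per arm is 1.96 × √(2/n):

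- n = 20: 1.96 × √0.100 = 0.62 SD
- n = 40: 1.96 × √0.050 = 0.44 SD
- n = 64: 1.96 × √0.03125 = 0.35 SD

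Every interim look on this calendar has at most 64 per arm, so a 0.3 SD threshold never adds a restriction. A 0.5 SD threshold starts to bind only above 31 per arm (1.96 × √(2/31) = 0.50).

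**If *clear* means a stricter interim level, with 0.05 at the end.** For 5, 10 and 20 equally spaced looks, p<0.01 at interims gives 6.5%, 7.6% and 9.0%; p<0.001 gives 5.1%, 5.3% and 5.3%. On the calendar schedules the ranges are about 6–10% and 5–6%.

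**Exaggeration.** With a true effect of 0.3 SD, quarterly looks (7 + 1) and a 0.3 SD threshold, half of trials stop early, at a median of 54 completers, with a mean estimate of 0.63 SD. With 5, 10 and 20 equally spaced looks the mean estimate at an early stop is 0.54, 0.58 and 0.62 SD, that is 1.8 to 2.1 times the truth.

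**Timeline sensitivity.** The dates give three different enrolment windows, counted from June 2020.

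- 4.m: 36 months, as above. A patient enrolled in late May 2023 would reach 12 months in about June 2024, after data collection ends on 31 May 2024.
- 2.g, last 12-month visit in July 2023: about 37–38 months less 13, so enrolment of about 24–25 months. Half-yearly to monthly looks over 24 months give 11.7% to 20.0%.
- 5.d, last visit in June 2022: about 24 months less 13, so enrolment of about 11 months. Almost no 12-month data would exist before enrolment closed, and the early stop could hardly operate.

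**The case against.** The strongest reply is that the protocol nowhere says it will test at plain 0.05. It asks for superiority that is clear, and both statistically and clinically significant, and an unseen analysis plan may define the looks and a boundary. That stands as a limit on the size: all the percentages are conditional. It does not remove the defect, because the stated rule is open-ended and binding and contains no stricter early criterion.

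Some stronger readings are tempting but not supported:

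- *The trial stops at the first p<0.05.* It does not; the rule also requires clinical significance and the word *clear*.
- *The error rate is 15–25%.* Neither that range nor 5% is in the protocol. Yearly looks give 11%, a strict interim level gives 5–6%, and a shorter enrolment period gives less inflation.
- *The Watch would be falsely declared superior that often.* The rates count false wins for either arm.
- *Clinical significance gives no protection.* A modest threshold gives none here, but 0.5 SD lowers the rate somewhat.
- *Recruiting surgeons will see results by arm.* The protocol does not say who runs the analyses, so this is inference.
- *The stop saves almost nothing.* That depends on when it happens. At 100 completers (month 100/5.56 + 13 = 31) about 172 are enrolled and 28 are saved. At 50 completers (month 22) about 122 are enrolled and 78 are saved.

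**Conclusion.** The point holds in conditional form. Sections 2.g and 5.d fix open-ended looks with a mandatory superiority stop, no cap on looks and no stronger early evidence. At two-sided 0.05 per look and 36 months of enrolment, the overall false-positive rate is about two to five times nominal: 11% (yearly) to 25% (monthly), or about 9–22% with a 0.5 SD clinical threshold. Effects from early stops would be overstated, about twofold for a true 0.3 SD.

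These figures rest on the assumed level, look schedule, even accrual, a single outcome and the 4.m calendar. The rule names no outcome, so applying it to several would raise the error further. The conflicting completion dates mean that the number of possible looks cannot be settled from the document.

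**What to change.** Amend 2.g, 5.d and the interim analysis mentioned in 4.m together, in one of two ways:

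1. Delete the Cohort 1 early superiority stop and compare the arms once, after the last 12-month visit. Section 2.b rates the Watch as minimal risk, so the protocol gives no safety reason for stopping early for benefit.
2. Keep one pre-specified look, for example when 100 patients have 12-month data, on a named outcome with an O'Brien-Fleming-type boundary: about p<0.003 at the look and p<0.049 at the end. This holds the overall two-sided error at 5%.

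Under either option, reconcile the completion dates (July 2023, June 2022, May 2024) and align 4.m, which promises only 6-month follow-up on everyone, so that 12-month data are collected on all patients.

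The cost is a short amendment to three sections and a slightly longer data collection period if the 4.m enrolment dates stay. What is lost is the chance of an earlier stop: on the 4.m calendar about 28 enrolments at 100 completers, and about 75–78 at around 50. Option 2 keeps the first of these.

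### Both cohorts must stop early on a significant result, but the stopping rule sets nothing that controls false positives and does not say whether enrolled patients are still followed

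*Protocol*

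**What the plan says.** Section 2g (Study Endpoint(s)) opens the Cohort 1 data to repeated analysis: "As participants reach the 12-month study period, we will conduct ongoing analysis of the data". It then makes stopping obligatory: "If we observe clear statistically significant and clinically significant superiority in one group, the study will be terminated". The main clause in full is "the study will be terminated prior to the projected total participant population has been enrolled". For Cohort 2 the trigger is a change, not a difference between groups: "If we observe clear statistically significant and clinically significant changes, the study will be terminated". Section 5d (Study Conclusion) repeats both rules and states ongoing analysis for Cohort 2 as well.

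No deciding outcome is named. The study endpoint in 2g is a time point: 12 months for Cohort 1 and 2–3 weeks for Cohort 2. Section 2a gives all Cohort 1 patients quality-of-life questionnaires and "an additional study-specific questionnaire regarding satisfaction with their care and recovery". Section 2g adds a form for one arm only: "Patients with the Apple Watch will also fill out a paper questionnaire assessing satisfaction with the Apple Watch".

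The Cohort 1 calendar appears in three forms:
- 2g: "the Cohort 1 will terminate after the all patients have had their 12-month postoperative visit, likely July 2023".
- 5d: the same event in June 2022.
- 4m: "June 1, 2020 - May 31, 2023: Screen and enroll new patients", with data collected to 31 May 2024, a minimum of six months' follow-up for everyone, and an interval analysis that is not described.

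**The concern.** A rule that obliges the team to stop on significance, under analysis of unstated frequency, gives chance several opportunities to trigger it. The protocol sets no limit on looks, no adjusted significance level, no size for clinical significance and no single outcome, and it refers to no other document for them.

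The meaning of a stop is also open. The wording can mean that recruitment closes while enrolled patients continue to 12 months. It can equally mean that the study and its analysis end there. The two readings have very different error rates.

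At stake is the between-arm comparison: Objective 4, and the satisfaction and self-reported outcomes in the hypothesis in section 1a. Objectives 1–3 are not between-arm tests, but an early stop would leave them with fewer patients. In Cohort 2, 15 patients have no control group and all are under back treatment. A change there cannot be attributed to the watch, so it is a poor reason to stop.

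**Working it through.** The protocol states no alpha, effect size or boundary, so there is no figure of its own to reproduce. The check asks what the rule does under labelled assumptions.

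**Inputs from the protocol.** 100 per arm (4a); 1:1 allocation (2a); 36-month enrolment window (4m); 12-month outcome plus 2–6 weeks before surgery (2a, 2g), taken as a 13-month lag; 15 patients in Cohort 2 (4a). About 24 months of accrual follows if 2g's July 2023 end date is taken back 13 months to June 2022, from a June 2020 start.

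**Assumptions.** One normal outcome, uniform accrual, two-sided 5% at every look and at the end, looks only while enrolment is open, and clinical significance taken as an observed 0.5 SD.

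**Test.** With n per arm, the trial is significant if |difference|/SD exceeds about 1.96 × √(2/n):
- n = 17: 0.67 SD
- n = 33: 0.48 SD
- n = 50: 0.39 SD
- n = 100: 0.28 SD

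The two conditions coincide at n = 2 × (1.96/0.5)² ≈ 31 per arm. Below that, a 0.5 SD requirement adds nothing, because significance already needs a larger difference.

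**Cohort 1 false positives, %** (two-sample t-tests, 40,000–80,000 simulated trials per scenario, simulation error about 0.2 points or less). The first three result columns assume analysis ends at the stop.

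| Accrual | Looks, per arm with 12-month data | No threshold | 0.5 SD for the stop only | 0.5 SD at every test | Enrolled patients followed, no threshold |
|---|---|---|---|---|---|
| 36 months | 50 | 8.4 | 5.8 | 1.5 | 5.3 |
| 36 months | 33 | 8.9 | 8.5 | 4.6 | 5.4 |
| 36 months | 17, 33 | 11.9 | 11.9 | 8.1 | 5.7 |
| 36 months | 17, 33, 50 | 13.6 | 11.7 | 8.5 | 5.8 |
| 24 months | 25 | 9.0 | 9.0 | 5.1 | 5.1 |
| 24 months | 12, 25, 38 | 14.2 | 13.5 | 10.0 | 5.2 |

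With enrolled patients followed, 0.5 SD for the stop only gives 5.1–5.7%, and 0.5 SD at every test gives 0.1–0.5%. Very early looks push the no-threshold rate to about 15.5% and the every-test rate to about 12%.

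**Choice of outcome.** With two outcomes (correlation 0.5) and looks at 17, 33 and 50 per arm, the rate is 23.7% without a threshold and 15.3% with 0.5 SD at every test. With no looks it is 9.1%.

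**Exaggeration.** With a true effect of 0.3 SD, trials that stop report on average 0.53–0.78 SD if analysis ends there, and 0.42–0.48 SD if enrolled patients are followed.

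**Cohort 2, no true change** (one-sample t-test, 200,000 trials). Tests after 5, 10 and 15 patients give 11.3%. A test after each of patients 5 to 15 gives 16.6%, as an upper case. If 0.5 baseline SD is also required, three tests give 9.3%, 6.2% or 3.4% at pre–post correlation 0.5, 0.7 or 0.8.

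**Can a look fall before enrolment closes?** Take a look when 100 patients have 12-month data.
- 4m: 13 + 100/(200/36) = 31 months. By then 31 × 200/36 ≈ 172 are enrolled, leaving 28.
- 2g (24 months): 13 + 100/(200/24) = 25 months, after enrolment has closed.
- 5d: June 2022 less 13 months puts the last enrolment at about May 2021. The first 12-month result, from a June 2020 start, arrives about July 2021. The stop could never operate.

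**The case against.** The strongest objection is that looks, boundaries and thresholds commonly sit in an SAP, and one may exist unseen. That would answer a complaint of missing detail. Here, however, the protocol itself states a mandatory rule twice for each cohort. A boundary elsewhere would leave that commitment in place, and what happens to enrolled patients after a stop is trial conduct that belongs in the protocol.

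Second, the rule asks for a clear result that is both statistically and clinically significant, so figures on significance alone drop a stated condition, and 5% at each look may be too lenient a reading of clear. This has force. Reading it as p<0.01 at looks and p<0.05 at the end, on the 36-month schedules with analysis ending at the stop, gives about 5.5–7% on significance alone, 5.5–6.6% with 0.5 SD for the stop only, and 1.0–2.5% with 0.5 SD at every test. The threshold matters too: at nominal 5% and applied at every test, 0.3 SD gives 7–13% and 0.8 SD gives 0.01–2.8%. So some readings are safe. Nothing in the protocol selects them.

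Third, if a stop closes enrolment only, the rate is 5–6%. That is a fair reading, but the protocol does not state it. Section 4m promises only six months' follow-up against a 12-month endpoint and does not address an early stop.

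Cohort 2 is small and short, so less is at stake there. That lowers the priority of its rule but does not justify keeping it.

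**Conclusion.** The concern holds. The protocol commits both cohorts to an efficacy stop whose false-positive rate it does not control. For one Cohort 1 outcome and one to three looks at nominal 5%, the rate if analysis ends at the stop is 8–14% on significance alone, 6–14% with 0.5 SD for the stop only, and 1–10% with 0.5 SD at every test. It is 5–6% if everyone enrolled is followed and analysed. Even in that last case the effect is overstated in trials that stop.

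These figures rest on the assumed alpha, look times, accrual and threshold. They show that the rate is left to choices not yet made, not that inflation is certain. The conclusion itself does not depend on any one figure. The rule needs to be settled before outcomes are compared by arm, because unplanned looks cannot be undone afterwards.

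**What to change.** **Preferred.** Delete the efficacy-stop sentences for both cohorts from 2g and 5d, complete planned enrolment and follow-up, and keep ongoing review for harm.

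**Alternative, Cohort 1 only.** State all of the following:
- One look, when 100 patients have 12-month data.
- One named between-arm outcome that all patients complete, with its scoring and clinical threshold. An example is the 12-month score on the care-and-recovery satisfaction questionnaire in 2a. The watch-satisfaction form in 2g cannot serve, because controls do not fill it in.
- An O'Brien-Fleming boundary: two-sided p<0.0052 at the look and p<0.048 at the end. Simulated overall error is 5.0%.
- A stop ends enrolment only, and all enrolled patients are followed to 12 months and included in the final analysis.

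**In either case**, reconcile the Cohort 1 dates in 2g, 5d and 4m, and bring 4m's six-month minimum into line with the 12-month endpoint. A patient enrolled on 31 May 2023 with surgery 2–6 weeks later reaches 12 months in mid-June to mid-July 2024, after 4m's data collection ends.

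**Cost.** A wording amendment to 2g and 5d and one calendar. The sponsor gives up stopping at nominal significance and the enrolments that might save; under 4m the bounded look could save at most about 28 of 200. The boundary costs almost no power: 55.8% against 56.1% at a true 0.3 SD, and 79.9% against 80.2% at 0.4 SD.
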